The duration of standard local anesthetic formulations vary from 4-8 hours and administration can include single injections or continuous infusion catheters. Liposomal bupivacaine, Exparel®, has a prolonged duration of action of up to 96 hours. Studies have verified its safety with a very low risk of dysrhythmias, local tissue reaction, effects on wound healing or nerve toxicity. In the elective surgical setting, liposomal bupivacaine has been shown to have an opioid sparing effect, increased duration of analgesia, increased patient satisfaction, earlier discharge, and lower hospital cost. This formulation has not been studied in trauma patients and its novel use may impact practice in pain management of trauma patients. Patients may exhibit a lower opioid requirement with the use of the liposomal bupivacaine. In addition, this may reduce the incidence of untoward effects including respiratory depression, central nervous system depression, and gastrointestinal dysfunction, and subsequently speed recovery with improved mobilization and cooperation with physical therapy. To date, no studies have evaluated liposomal bupivacaine regional analgesia following extremity trauma. This pilot study aims to assess the

efficacy of long-acting liposomal bupivacaine compared to ropivacaine 0.2% in orthopedic trauma patients with acute pain following femur or hip fracture.

6) Inclusion and Exclusion Criteria

Inclusion criteria:

- 1) age \geq 18 years \leq 70 years
- 2) Patient's s/p trauma, with confirmed femur and/or hip fractures with a planned admission to the hospital.
- 3) Patient is ambulatory without assistance (e.g. walker, cane, caretaker) prior to incident.

Exclusion Criteria:

- 1) >10 hours since presentation to the emergency department
- 2) History of seizure disorder, recent seizure or a document intra-cranial hemorrhage.
- 3) Central or peripheral neurologic deficit on presentation
- 4) Concern or compartment syndrome
- 5) Associated additional long bone fractures
- 6) End stage liver failure
- 7) Renal failure requiring dialysis
- 8) Pregnancy or breast feeding
- 9) Prisoners
- 10) Coagulopathy with INR >1.5
- 11) Use of direct thrombin inhibitors (bivalirudin, argatroban, desirudin, dabigatran etexilate), or direct factor Xa inhibitors (rivaroxaban, apixaban, edoxaban)
- 12) Suspected prolonged intubation within first 12 hours secondary to respiratory failure other than peri-procedurally
- 13) Adults unable to consent

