15) Provisions to Monitor the Data to Ensure the Safety of Subjects

This study involves minimal risk to the patient, however, the DoD requires an independent research monitor for all clinical studies and thus a medical monitor will be assigned. [name], MD, Professor of Surgery and Vice Chair of Surgery will act as the Data Safety Monitor for this study. Any unanticipated adverse event meeting grade 3 or grade 4 as listed below per the FDA's guidance for industry, will be reported to the study medical monitor. The medical monitor will keep a database of the reported events and will report any of the above adverse events to the FDA's MedWatch. In addition, subjects having experience an adverse

event of Grade 3 or 4 will be followed by the PI for the duration of their hospitalization.

The greatest risk for systemic toxicity is at the time of administration and most often as a result of inadvertent intravenous injection of the drug with rapid onset of symptoms. The procedure will be performed per UCDMC's "Hip Fracture Protocol" which includes routine fascia iliaca compartment blocks, a provider training protocol and routine ultrasound guidance. The protocol also includes telemetry monitoring, continuous pulse oximetry and q 15 min neurologic assessments for 30 min following injection. In addition, the patients will remain on telemetry for an additional 4 hours monitoring for any delayed events.

Following this 4 hour period, evaluation and capture of adverse events will continue until the completion of the 96 hour study period. This will consist of nursing evaluation and vitals every 4 hours around the clock and on an as needed basis. The study coordinator will evaluate for any potential events on a daily basis throughout the study period. The PI or co-PI will be notified directly of any severe adverse event at the time of the event.

The definitions of an adverse event are in line with the WHO-UMC system for standardized case causality assessment.

Causality term	Assessment criteria*
Certain	
• Event or laboratory test abnormality, with plausible time relationship to drug intake• Cannot be explained by disease or other drugs• Response to withdrawal plausible (pharmacologically, pathologically)• Event definitive pharmacologically or phenomenologically (i.e. an objective and specific medical disorder or a recognised pharmacological phenomenon)• Rechallenge satisfactory, if necessary

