Incidence 1 to 5%: Urinary retention, dizziness, rigors, hypertension, tachycardia, anxiety, oliguria, hypoesthesia, chest pain, hypokalemia, dyspnea, cramps, and urinary tract infection.

There is also the potential risks of severe life-threatening adverse effects associated with the administration of local anesthetics which are due primarily to toxic systemic concentrations. Risks are associated with toxic plasma concentrations and can be characterized as central nervous system, cardiovascular and allergic reactions and local tissue toxicity. Despite the sustained release and potential for systemic toxicity, in studies to date, the safety profile of Exparel does not appear to differ in a clinically significant way from standard bupivacaine HCl. For the doses studied as part of the FDA clinical development program, there is no evidence that Exparel produces tissue toxicity in the short or long term, that it adversely affects wound healing, or that it is any more likely than bupivacaine HCl to cause neurological or cardiac toxicity with systemic absorption or inadvertent injection.

The greatest risk for systemic toxicity is at the time of administration and most often as a result of inadvertent intravenous injection of the drug with rapid onset of symptoms. As a result, FICBs will be administered in the emergency room where trained personnel and equipment are available to promptly treat patients who show evidence of neurological or cardiac toxicity. The procedure will be performed per UCDMC's "Hip Fracture Protocol" and will include telemetry monitoring, continuous pulse oximetry and q 15 min neurologic assessments for 30 min following injection. In addition, the patients will remain on telemetry for an additional 4 hours for monitor for any delayed events. The FICB is performed laterally, distant from the neurovascular bundle, and under ultrasound guidance minimizing the risk of intravenous injection. The lipid emulsion of the liposomal bupivacaine results in a white milky appearance similar to that of propofol. Steps taken to minimize inadvertent medication error include a recent manufacture change in propofol labeling and storage, handling and delivering of the study drug by the IDS at UCDMC. Patients that exhibit any of the signs or symptoms listed in 16b, will be removed from blinding and 20% lipid emulsion will be administered.

Privacy Risk

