drug service (IDS) at UCDMC. Following informed consent, patients will undergo computer generated, blinded block, 1:1 randomization. The blinding will be maintained up to the time of breaking the seal for drug administration. Necessary measure will be followed to maintain patient blinding. An ultrasound guided fascia iliaca compartment block (FICB) with either 266mg (60 ml) of liposomal bupivacaine or 120mg (60 ml) of 0.2% ropivacaine. Both groups will be able to receive as needed analgesia per the primary attending service. (e.g., oral hydrocodone/acetaminophen 5/325 mg or narcotic IV push as needed for breakthrough pain). Patients will remain blinded throughout the hospitalization.

a) The involved drugs are:

- i) Liposomal bupivacaine (Exparel®, Pacira Pharmaceuticals, Parsippany, NJ) is a long-acting formulation of bupivacaine HCl, an amide-type local anesthetic/analgesic that is FDA approved for single dose infiltration into a surgical site to provide post-surgical analgesia. After local administration, bupivacaine is slowly released from the liposomes resulting in prolonged plasma levels and analgesia for 96 hours.
- ii) Ropivacaine HCl(Naropin®, AstraZeneca Pharmaceuticals) is an amide-type local anesthetic/analgesic which is FDA approved for local and regional anesthesia for acute pain management. This includes local infiltration, regional nerve and epidural blocks, both single dose and continuous infusion.

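### No neurologic or injection-site check of the blocked leg is named after 30 minutes, neither harm has an item or grade, and the capture windows conflict, so a persisting deficit could be missed, more easily in the liposomal arm

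*Combined protocol and SAP*

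**What the plan says.** **Checks after the block.** Section 15 provides "q 15 min neurologic assessments for 30 min following injection", and Section 17 repeats this. Both sections place it next to the risk of systemic toxicity from inadvertent intravenous injection. Section 15 then says "the patients will remain on telemetry for an additional 4 hours monitoring for any delayed events".

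**Capture after that.** Section 15: "evaluation and capture of adverse events will continue until the completion of the 96 hour study period". On content: "This will consist of nursing evaluation and vitals every 4 hours around the clock and on an as needed basis". And: "The study coordinator will evaluate for any potential events on a daily basis throughout the study period".

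**A different end of capture.** Section 12 has adverse effects collected prospectively from the block to the end of the hospital stay, as fits each endpoint. Section 10 makes participation last as long as the hospital stay. Section 15 itself has Grade 3 or 4 events followed for the whole hospitalization.

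**Duration of effect.** Section 5 gives 4-8 hours for standard local anesthetics and a maximum of 96 hours for the liposomal drug. Section 30 describes the latter as "resulting in prolonged plasma levels and analgesia for 96 hours".

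**The harms in question.** Section 17 classes the risks of toxic plasma levels as "central nervous system, cardiovascular and allergic reactions and local tissue toxicity". Section 5 mentions "local tissue reaction, effects on wound healing or nerve toxicity", but as effects whose risk was found to be very low.

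**The concern.** Section 5 says the liposomal product has not been studied in trauma patients, and the approved use cited in Section 30 is infiltration of a surgical site. A pilot using it for a fascia iliaca block is a natural place to look for nerve or local tissue harm. While a block is working, new numbness or weakness in that leg may be taken for the intended effect. The informative time to look is after the block resolves, and the plan schedules nothing specific then.

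Two things are at stake. First, a report of no nerve or tissue harm could reflect the absence of a directed examination rather than the absence of harm. Second, ascertainment could differ between arms because the blocks end at different times within a common window. Section 4 says the results will guide larger multicenter trials, so an unexamined zero could be carried forward as safety evidence.

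**Working it through.** The plan gives no figure of its own on this point, so there is none to reproduce. The check sets the schedule against the stated durations and then looks for a route by which either harm would be recorded and graded.

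**1. Named checks.** Every 15 min for 30 min gives 30/15 = 2 neurologic checks. No later one is named. No injection-site examination is named at any time. From 4 h to 96 h there are (96 - 4)/4 = 23 general nursing evaluations plus the daily coordinator review, with no leg or injection-site item specified.

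**2. Capture time left after the block ends, under the 96 h window.** Assumptions: the clock starts at injection, and ropivacaine 0.2% behaves as a standard agent.

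| Arm | Stated duration | Capture left after block |
|---|---|---|
| Ropivacaine | 4-8 h | 96 - 8 = 88 h to 96 - 4 = 92 h |
| Liposomal, at stated maximum | 96 h | 96 - 96 = 0 h |

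A liposomal block that ends sooner leaves more than 0 h.

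**3. The same under the hospital-stay window.** Time after the block then depends on length of stay, which the documents do not give. A patient discharged before 96 h leaves observation within the liposomal drug's stated maximum duration. No contact after discharge is described in the sections available.

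**4. Recording and grading.**
- The adverse effects listed in Section 12 are hypertension, hypotension, tachycardia, bradycardia, respiratory depression, emesis, hallucinatory reactions and pruritus. Neither harm is among them.
- The severity table was adapted to the study and has a row even for methemoglobinemia. It has none for motor or sensory deficit or for an injection-site reaction.
- Reporting to the medical monitor and investigator follow-up (Section 15) and the study stopping rule (Section 12) all depend on Grade 3 or 4. An event without a row has no defined path to any of them.

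**5. What a zero would mean.** With all 17 patients in an arm examined and no event seen, the exact two-sided 95% upper limit is 1 - 0.025^(1/17) = 0.195, or 19.5%. With fewer examined, the limit is higher.

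**The case against.** The strongest reply is that the plan does not stop looking. Nurses evaluate every 4 hours, the coordinator reviews daily, and Section 12 extends collection to the whole stay. Section 12 introduces its list as examples, so it is not closed. Paresthesia triggers unblinding under Section 16b, and ambulation and chronic pain reports are collected. Section 5 calls these risks very low, and Section 17 reports no evidence of tissue toxicity at the doses studied in the development programme.

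Much of this stands. A reader might infer that a lasting deficit would certainly go unreported. The documents do not support that: general surveillance of an inpatient could pick it up. Nor do they support a firm 96 h cut-off, since two sections point to the hospital stay. The stated 96 h is a maximum and, in Section 30, refers to analgesia; the documents do not say that motor or sensory block lasts as long. The masking argument does not extend to an injection-site reaction, which is visible at any nursing evaluation.

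A reader might also infer that a case is likely among 17 patients. The documents give no rate for a lasting deficit. At assumed rates of 0.5% and 1%, the chance of at least one case, 1 - (1 - p)^17, is 8% and 16%. The point does not depend on a case being likely.

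What the reply does not answer is that neither harm has a named item, a grade or an examination timed to block resolution. Section 16b treats paresthesia as a sign of systemic toxicity, not as a persisting deficit. The chronic pain report has no time point and is a different outcome. A longer window alone would not supply what is missing.

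**Conclusion.** The point holds as a gap in ascertainment and an internal inconsistency. Three facts rest on the text alone: no neurologic or injection-site check is named after 30 minutes; neither harm appears in the adverse-effect list or the severity table; and the end of capture is 96 h in one section and the hospital stay in two others.

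The imbalance between arms is conditional. It is about 88-92 h against about 0 h of capture after the block if the 96 h window governs and the liposomal block lasts its stated maximum. It shrinks if the block ends earlier or if the hospital-stay window governs and patients stay beyond 96 h. The supportable conclusion is that a persisting motor or sensory deficit could be missed, and more easily in the liposomal arm. For an injection-site reaction, the gap is only the missing item and grade. The primary opioid endpoint is not affected.

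**What to change.** 1. Reconcile Sections 10, 12 and 15 into one adverse-event capture window that applies to both arms, and state when its clock starts.
2. Have the blinded coordinator, who already reviews patients daily, record two items from existing nursing and physician examinations: motor and sensory status of the blocked leg, and the injection site. Record them at about 96 h if the patient is still in hospital and again at discharge, with the time since injection. Exclusion 3 removes patients with a deficit on presentation, so a recorded deficit is new since presentation.
3. In the Statistical Analysis text (Section 14), report counts per arm with exact 95% confidence intervals, using the number actually examined as denominator, and note that 0/17 still leaves an upper limit of 19.5%.
4. Have the sponsor and medical monitor state how these events are graded and how they relate to the stopping rule in Section 12. That decision is theirs; no grade is proposed here.

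The cost is two case-report-form items completed by existing staff, plus a protocol edit. There are four downsides. Some deficits will come from the injury or its surgery, and 17 per arm cannot separate these causes well. Any new grade interacts with a rule that stops the study on two matching Grade 3 reactions, or one Grade 4 or higher, so the change is not merely clerical. Existing examinations may not always document the leg, which is why the number examined must be reported. Recording to discharge cannot show how long a deficit lasts afterwards.

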- (1) If a subject experiences an adverse event (AE) that renders them incapable of continuing with the remaining study assessments, the subject is to be discontinued. A final evaluation will be performed so that the subject's study participation can be terminated in a safe and orderly manner.
- (2) Patients will be free to discontinue the study at any time, without prejudice to future treatment. These subjects will be encouraged to complete at least the remaining safety assessments.
- (3) Patients will be removed from the study if they refuse either the study drug administration or fail to comply with study procedures.
- (4) In the event that a subject chooses to withdraw from research after data collection has been performed, no additional data will be collected after time of withdrawal.
- (5) There are no foreseeable circumstances necessitating the withdrawal of subjects from research without their consent.

b) Unblinding Criteria

- (1) The blinding of therapy administered will be removed during the study period if evidence of local anesthetic toxicity is present based on the following:
 - (a) Central nervous system reactions manifested by one of the following: paresthesia, acute anxiety, tinnitus or seizure.
 - (b) Cardiac reactions manifested by one of the following: life threatening arrhythmia (ventricular arrhythmia, new onset heart block, new onset QT prolongation, hypotension unresponsive to fluid resuscitation or requiring vasopressor support or CPR).
 - (c) Systemic Allergic reactions manifested by anaphylaxis.

17) Risks to Subjects

Pharmacologic risk:

Administrations of local anesthetics is common place in medical practice, however, there are adverse reactions. Those more frequent are listed below per each specific anesthetic.

Liposomal bupivacaine:

Very Common Adverse Reactions ($\geq 10\%$): nausea, constipation, and vomiting.

Common Adverse Reactions ($\geq 2\%$ to $< 10\%$): pyrexia, dizziness, edema, peripheral, anemia, hypotension, pruritus, tachycardia, headache, insomnia, anemia postoperative, muscle spasms, hemorrhagic anemia, back pain, somnolence, and procedural pain.

Ropivacaine:

Incidence of $\geq 5\%$ in all clinical studies (N=3988): hypotension (37%), nausea (24.8%), vomiting (11.6%), bradycardia (9.3%), fever (9.2%), pain (8%), postoperative complications (7.1%), anemia (6.1%), paresthesia (5.6%), headache (5.1%), pruritus (5.1%), and back pain (5%).

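### Sections 16b and 17, read literally, order unblinding and lipid emulsion for a single isolated paresthesia, acute anxiety or tinnitus, and automatic lipid emulsion for anaphylaxis

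*Combined protocol and SAP*

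**What the plan says.** Section 16 b) Unblinding Criteria opens: "The blinding of therapy administered will be removed during the study period if evidence of local anesthetic toxicity is present based on the following". Three groups of signs follow.

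- Group (a): "Central nervous system reactions manifested by one of the following: paresthesia, acute anxiety, tinnitus or seizure".
- Group (b): cardiac reactions, described as life-threatening arrhythmia and as hypotension that resists fluids or needs vasopressors or CPR.
- Group (c): "Systemic Allergic reactions manifested by anaphylaxis".

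The pharmacologic-risk text of Section 17 ends with the action rule: "Patients that exhibit any of the signs or symptoms listed in 16b, will be removed from blinding and 20% lipid emulsion will be administered".

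Section 17 also lists the more frequent reactions to each drug. For ropivacaine, paresthesia is given at 5.6% in the list of reactions seen in at least 5% of patients, and anxiety is in the next band: "Incidence 1 to 5%: Urinary retention, dizziness, rigors, hypertension, tachycardia, anxiety". The liposomal bupivacaine lists contain neither sign. Tinnitus is in neither drug's list.

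**The concern.** Two of the three milder group (a) signs are also on the protocol's own list of known ropivacaine reactions. The patients have an acute fracture, are in pain and have just had a nerve block, so an isolated tingling or an anxious episode has explanations other than systemic toxicity. Staff will be looking for such signs, because Sections 15 and 17 schedule "q 15 min neurologic assessments for 30 min following injection".

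Staff who follow the text to the letter would break the code and give a rescue drug for a non-specific sign. Staff who use their judgement would depart from the written protocol. At stake are a treatment given to a patient without an assessment step, and avoidable loss of the blind in a trial of 17 patients per arm. For anaphylaxis, the text orders lipid emulsion and names no other treatment.

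**Working it through.** The plan states no figure on this point, so there is none to reproduce. The check sets the trigger list beside the action rule and the reaction lists.

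**Step 1. What each trigger requires.**

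| 16b(1) item | Severity built in? | In the Section 17 ropivacaine lists? | Literal consequence |
|---|---|---|---|
| (a) paresthesia | No | Yes, 5.6% | Unblind and lipid emulsion |
| (a) acute anxiety | Only the word acute | Anxiety, 1 to 5% | Unblind and lipid emulsion |
| (a) tinnitus | No | No | Unblind and lipid emulsion |
| (a) seizure | Severe in itself | No | Unblind and lipid emulsion |
| (b) cardiac signs | Yes, in the wording | Hypotension, 37%, but (b) needs it to be refractory or to need vasopressors or CPR | Unblind and lipid emulsion |
| (c) anaphylaxis | Severe in itself | No | Unblind and lipid emulsion |

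The hypotension row is instructive. The protocol lists it as very frequent with ropivacaine and triggers only on a severe form. The first three rows have no comparable filter.

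**Step 2. Is a filter supplied elsewhere?** Section 15 has a causality scale with a category for events that disease or other drugs could also explain, and a severity table whose footnote calls for clinical judgement on bradycardia. Neither is linked to 16b, and the severity table as shown has no row for paresthesia, anxiety or tinnitus. Section 17 makes the lipid step subject to no condition other than presence on the list.

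**Step 3. Anaphylaxis.** Section 17 says that the toxicity risks "can be characterized as central nervous system, cardiovascular and allergic reactions and local tissue toxicity", so anaphylaxis as a reason to unblind fits the protocol's own scheme. The unconditional lipid order reaches it only because one sentence covers all of 16b. The documents give no separate treatment for it.

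**Step 4. Can the size be computed?** No.

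- The 5.6% and the 1 to 5% are pooled over all ropivacaine studies, without route, cause, timing or severity. Section 30 says that the drug is also used for epidural blocks and continuous infusion.
- No rate is given for these signs with liposomal bupivacaine.
- The arm size gives only the weight of one code-break, 1/17 = 5.9% of an arm. It does not say how many there would be.

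**The case against.** The strongest defence is that 16b is conditional: it speaks of evidence of toxicity and of reactions, and the anxiety must be acute. The Section 17 sentence closes a paragraph about patients who show neurological or cardiac toxicity. Read together, a clinician who first decides whether toxicity is present is a plausible reading. This stands in part. But 16b defines the evidence by the list, one sign is enough, and Section 17 drops the qualifier and says any sign. At best the two sections are ambiguous on an instruction to give a drug.

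A second defence is that a low trigger is prudent. Section 5 says that the product has not been studied in trauma, and under Section 12 the receiving team does not know the arm. This supports a low threshold for assessment, and it is why the remedy treats whenever toxicity cannot be excluded. It does not require an automatic drug for every isolated sign.

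Third, Section 6 excludes patients with a neurologic deficit on presentation or concern for compartment syndrome, so the injury is a less ready explanation for a new sign. That is fair, but the block itself and pain remain.

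Finally, the documents say nothing on the risks or indications of lipid emulsion. A reader might infer that the rule harms patients; that cannot be shown from them. The point is only that the order is unconditional.

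**Conclusion.** The concern holds in a narrow form. For isolated paresthesia, acute anxiety or tinnitus, the literal text makes unblinding and lipid emulsion mandatory with no severity, causality or judgement step. It also makes lipid emulsion automatic in anaphylaxis. This rests on reading Section 17 as written and on no overriding guidance in the institutional Hip Fracture Protocol, which is not among the documents. Severity is minor: a cheap improvement.

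Four stronger readings are tempting and are not supported.

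- **That all of 16b lacks a severity threshold.** Group (b) states one, and seizure and anaphylaxis are severe in themselves.
- **That about one ropivacaine patient would trigger the rule** (17 × 0.056 = 0.95). This carries a pooled rate over to this block and dose and treats every reported paresthesia as a trigger. Neither step is supported.
- **That the opioid endpoint is biased.** A late code-break could reach the primary service, which sets as-needed analgesia. But Section 17 puts the greatest toxicity risk at administration, when the emergency physician giving the block is already unblinded. No text withdraws unblinded patients or drops them from the analysis. The effect is possible, with no size that can be given.
- **That the rule should lapse once a standard block wears off.** Section 5 gives standard agents 4 to 8 hours, but block duration is not the period of toxicity risk, and Section 30 describes plasma levels of liposomal bupivacaine lasting 96 hours.

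**What to change.** Reword 16b(1) and the last sentence of the Section 17 pharmacologic-risk text together, along these lines:

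- *Seizure, or any sign in 16b(1)(b): the blind is broken and 20% lipid emulsion is given, as now.*
- *Isolated paresthesia, acute anxiety or tinnitus: the treating clinician assesses the patient immediately. If the clinician judges the sign to represent systemic local anesthetic toxicity, or cannot exclude it, the blind is broken and 20% lipid emulsion is given.*
- *Anaphylaxis, 16b(1)(c): the blind is broken and the patient is managed for anaphylaxis. Lipid emulsion is not automatic.*

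Do not add a time cut-off.

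The cost is wording in two sections, with no extra patients, visits, staff or data. The downside is that an isolated early central nervous system sign is assessed before lipid emulsion is given, so treatment could start slightly later. Treating when toxicity cannot be excluded keeps that risk small.
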